10 STATISTICS

10.1 Analysis Populations

The Full Analysis Set (FAS) includes all subjects who received at least 1 dose of study drug. FAS analyses will be conducted on the basis of the randomized treatment. All efficacy analyses will be assessed using the FAS.

A Per-Protocol Set (PPS) will also be used to analyze efficacy endpoints and will be based on study drug exposure (compliance and/or time on study drug) and major protocol deviations. The criteria for inclusion in the PPS will be finalized and documented in the statistical analysis plan (SAP) prior to database lock.

The Safety Set (SAF) includes all randomized subjects who received at least 1 dose of study drug. The SAF will be conducted on the basis of the actual treatment received. All safety analyses will be assessed using the SAF.

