Definition of PD	Progressive disease is assessed if the sum of the diameters has increased by ≥20% and ≥5 mm from nadir (including baseline if it is the smallest sum). Patients with measurable disease: for "unequivocal progression" based on non-target disease, there must be an overall level of substantial worsening that merits discontinuation of therapy (if target disease is SD/PR). Patients without measurable disease: for "unequivocal progression" of non-target disease, the increase in overall tumor burden must be comparable to the increase required for PD of measurable disease.
Assessment of new lesions	New lesions should be unequivocal and not attributable to differences in scanning technique or findings which may not be tumor (ie, 'new' bone lesions may be healing or flare of preexisting lesions). If one is equivocal, repeat scans are needed to confirm. If confirmed, PD is assessed at the date of the initial scan. Lesions identified in anatomic locations not scanned at baseline are considered new. New lesions on ultrasound should be confirmed on CT/MRI.
CR = complete response; CT = computed tomography; FDG-PET = positron emission tomography with fluorodeoxyglucose; LD = longest diameter; MRI = magnetic resonance imaging; PD = progressive disease; PET = positron emission tomography; PR = partial response; RECIST = Response Evaluation Criteria in Solid Tumors; SAD = short axis diameter; SD = stable disease.	

RECIST v1.1	
FDG-PET	New lesions can be assessed using FDG-PET: (-) PET at baseline and (+) PET at follow-up is PD based on a new lesion. No PET at baseline and (+) PET at follow-up is PD if the new lesion is confirmed on CT. If a subsequent CT confirms the new lesion, the date of the PD is the date of the initial PET scan. No PET at baseline and (+) PET at follow-up corresponding to pre-existing lesion on CT that is not progressing; not PD.
Recurrence of lesions	For a patient with SD/PR, a lesion which disappears and then reappears will continue to be measured and added to the sum. Response will depend upon the status of the other lesions. For a patient with CR, reappearance of a lesion would be considered PD.
Overall response	One overall response table integrates target, non-target and new lesions and another table integrates non-target and new lesions for the assessment of subjects without measurable disease.

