- C. Patients with CA-125 in the normal range pretreatment must show evidence of CA-125 greater than, or equal to, two times the upper normal limit on two occasions at least one week apart.

Elevated values must be confirmed by two separate measurements obtained at least one week apart. CA 125 progression will be assigned the date of the first measurement that meets the criteria as noted. Patients are not evaluable by CA 125 if they have received mouse antibodies (unless the assay used has been shown not to be influenced by HAMA^{4,5}) or if there has been medical and/or surgical interference with their peritoneum or pleura during the previous 28 days.

A patient may be declared to have progressive disease on the basis of either the objective RECIST criteria or the CA 125 criteria. The date of progression will be the date of the earlier of the two events if both are documented

Definition of progression after first-line therapy in ovarian cancer as proposed by the GCIG

GCIG subcategorized group	RECIST Measurable/non-measurable disease		CA 125
A	Compared to baseline (or lowest sum while on study if less than baseline), a 20% increase in sum of longest diameters (RECIST definition) or Any new lesions (measurable or non-measurable) Date PD: date of documentation of increase or new lesions	A N D / O R	CA 125 $\geq 2 \times$ ULN documented on two occasions # Date of PD: first date of the CA 125 elevation to $\geq 2 \times$ ULN
B	As for A		CA 125 $\geq 2 \times$ nadir value on two occasions # Date of PD: first date of the CA 125 elevation to $\geq 2 \times$ nadir value
C	As for A		As for A

GCIG groups A, B & C defined above.

Repeat CA 125 any time, but normally not less than 1 week after the first elevated CA 125 level. CA 125 levels sampled after patients received mouse antibodies (unless the assay used has been shown not to be influenced by HAMA^{4,5}) or if there has been medical and/or surgical interference with their peritoneum or pleura during the previous 28 days, should not be taken into account.

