6.4. Demographic and Baseline Characteristics

Subject demographics will be summarized for age (years), sex, ethnicity, race, baseline height (cm), baseline weight (kg), BMI (kg/m²), and BSA (m²). Age will also be categorized as a categorical variable (age < 65, ≥ 65 years) for reporting.

The following conversions and equations will be used as applicable:

- Height (in cm) = height (in inches) * 2.54
- Weight (in kg) = weight (in lbs) * 0.4536
- BMI (kg/m²) = weight(kg)/[height(m)²]
- BSA(m²) = $\sqrt{[(\text{height}(\text{cm}) * \text{weight}(\text{kg}))/3600]}$

Duration of time from initial diagnosis to screening (in months); cancer type; histology; genetic mutations; TNM staging at diagnosis; TNM staging at study entry; stage at diagnosis; stage at study entry; disease specific genetic mutations; prior systemic therapy, prior radiation and prior surgery (Yes/No); sum of target lesions per RECIST 1.1 at baseline (mm); baseline CA-125 (and response evaluability per GCIG as Yes/No as identified in Section 7); and baseline ECOG will be summarized. Histology and genetic mutations for phase 1 patients will be provided by Aduro outside of the clinical database.

Subject demographics and baseline characteristics, including cancer related surgeries, systemic therapies, and prior radiotherapy, will be listed.

Sponsor: Aduro Biotech, Inc.
Protocol Number: ADU-CL-11
Version and Date: Version 1.0, 03MAY2018

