Progressive serial elevation of serum CA-125 will be used to determine CA-125 response. Guidelines for using CA-125 response have been developed and are based on the Gynecological Cancer Intergroup (GCIIG) Definitions for Response and Progression. Subjects should have a pre-treatment CA-125 of at least twice the ULN in order to be considered for CA-125 response assessment. Subjects are not evaluable by CA-125 if they have received mouse antibodies or if there has been medical and/or surgical interference with their peritoneum or pleura during the previous 28 days. In those subjects considered evaluable by CA-125, a CA-125 response would be obtained the moment the CA-125 is reduced by 50% and this should be confirmed with a consecutive CA-125 assessment not earlier than 28 days after the previous one; the date of the first 50% reduction to be the reference date for the CA-125 response.

Progression is conventionally defined according to RECIST 1.1 but can also be based on serum CA-125. In assigning the date of progression, PD by objective change in tumor size should always take precedence over CA-125 should it occur first. If measurable disease is reducing in size during treatment but the CA-125 results suggest progression, the patient should continue to receive protocol treatment. If measurable disease is stable but CA-125 indicates confirmed progression over at least 4 weeks, may advise changing protocol treatment, unless there is the possibility that the therapy could be slowing the rate of rise of CA-125. CA-125 progression is defined as:

- Elevated CA-125 pretreatment and normalisation of CA-125 must show evidence of CA-125 greater than, or equal to, two times the upper normal limit on two occasions at least one week apart or
- Patients with elevated CA-125 pretreatment, which never normalises must show evidence of CA-125 greater than, or equal to, two times the nadir value on two occasions at least one week apart or
- Patients with CA-125 in the normal range pretreatment must show evidence of CA-125 greater than, or equal to, two times the upper normal limit on two occasions at least one week apart.
- Elevated values must be confirmed by two separate measurements obtained at least one week apart. CA 125 progression will be assigned the date of the first measurement that meets the criteria as noted.

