Subjects which do not have measurable disease at study entry will be evaluated based on GCIG criteria and will not be included in mRECIST and RECIST 1.1 analyses; endpoint derivations will be considered not evaluable (NE). Subjects which are not evaluable per GCIG CA-125 criteria will be handled similarly.

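### The SAP's not-evaluable rule is not limited to response, so some subjects get no PFS under a criterion even when progression or death could be scored

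*SAP*

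**What the plan says.** SAP section 7 closes with a handling rule. Subjects without measurable disease at entry are evaluated by GCIG criteria and "will not be included in mRECIST and RECIST 1.1 analyses; endpoint derivations will be considered not evaluable (NE"). The next sentence extends this to the other criterion: "Subjects which are not evaluable per GCIG CA-125 criteria will be handled similarly". Section 7.1 then derives best overall response (BOR), ORR, PFS, DCR and DOR, and repeats PFS under RECIST v1.1 and GCIG.

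On CA-125, SAP section 7 attaches the baseline threshold to response: "Subjects should have a pre-treatment CA-125 of at least twice the ULN in order to be considered for CA-125 response assessment". SAP section 6.4 plans one baseline flag, "response evaluability per GCIG as Yes/No as identified in Section 7". No separate flag for progression is defined.

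Progression has its own rules. In the SAP the third of these reads "Patients with CA-125 in the normal range pretreatment must show evidence of CA-125 greater than, or equal to, two times the upper normal limit". Two such values are needed, taken no less than a week apart. Protocol Appendix C contains the same rule as its group C. SAP section 7 also allows progression to be declared by RECIST or by CA-125, dated at the earlier.

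For patients without measurable disease, protocol Appendix B defines progression on non-target disease: "the increase in overall tumor burden must be comparable to the increase required for PD of measurable disease". It also refers to a response table for them built from non-target and new lesions.

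On population, protocol section 10.1 defines the full analysis set (FAS) as all subjects with at least one dose and states: "All efficacy analyses will be assessed using the FAS".

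**The concern.** Being unable to show a response and being unable to show progression are different things. Measurable disease and a raised baseline CA-125 are needed to measure shrinkage or a fall. They are not needed to observe a new lesion, clear worsening of non-target disease, or death. A rule that makes every endpoint under a criterion NE carries a response condition over to PFS.

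Two things are at stake. First, PFS listed under the three criteria would cover different sets of subjects, selected on baseline characteristics, and the plan does not say so. Second, the NE sentence conflicts with progression rules elsewhere in the same section, so two programmers could derive different GCIG PFS entries for the same subject.

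**Working it through.** No figure in either document rests on this rule, so there is nothing to reproduce. The check sets the passages side by side.

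**Step 1: who is covered.** Protocol section 4.1, inclusion criterion 3, requires measurable disease but lets Phase 1 admit subjects without it if they are assessable by GCIG CA-125. The first NE sentence therefore reaches Phase 1 only. The second reaches both phases.

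**Step 2: what happens to PFS.**

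| Subject and outcome | Rule elsewhere | Under the NE sentences |
|---|---|---|
| No measurable disease; new lesion or clear non-target worsening | Progression, protocol Appendix B | No mRECIST or RECIST PFS |
| No measurable disease; dies without progression | Event, protocol 10.2.1.2 and SAP 7.1 | No mRECIST or RECIST PFS |
| Not GCIG-evaluable; RECIST progression | Progression by either route, SAP 7 | No GCIG PFS |
| Not GCIG-evaluable; dies without progression | Event, protocol 10.2.1.2 and SAP 7.1 | No GCIG PFS |
| No assessment of progression | Censored at first dose, protocol 10.2.1.2 | NE if the subject is in either group |
| Normal baseline CA-125; two values at or above 2 x ULN at least a week apart | Progression, third SAP rule and Appendix C group C | Unclear: depends on the meaning of not evaluable |

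In the first four rows an event that the plan knows how to date is discarded. In the fifth, the protocol keeps the subject and censors; the SAP removes the subject.

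**Step 3: does not evaluable per GCIG include a low baseline CA-125?**

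- For: the only planned flag is a response evaluability flag taken from SAP section 7. Appendix C, under its definition of response, allows evaluation by CA-125 only with a pre-treatment value of at least twice the upper limit.
- Against: SAP section 7 uses the words not evaluable only for mouse antibodies or recent interference with the peritoneum or pleura, and ties 2 x ULN to response. The progression part of Appendix C repeats the antibody and interference exclusion and sets no baseline threshold.

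The three CA-125 progression rules cover every baseline: raised and later normalised, raised and never normalised, and normal. None requires a baseline of 2 x ULN. If low baseline counts as NE, the third rule has no one to apply to in GCIG PFS, and the first two lose subjects between 1 and 2 x ULN. If it does not count, all three rules work, and the NE sentence still removes RECIST progression and deaths for subjects with antibodies or interference. For those subjects Appendix C only says that the affected CA-125 values should be disregarded.

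**Step 4: is the departure declared?** SAP section 9 lists one change: efficacy endpoints are derived and listed but not summarised. The exclusion from PFS is not mentioned.

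**Step 5: what is not affected.** Phase 2 subjects must have measurable disease, and the primary endpoints and stage rules use mRECIST. For GCIG response endpoints, the 2 x ULN restriction agrees with Appendix C.

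**The case against.** The strongest reply is that little turns on this. Efficacy is listed and not summarised, no figures or tests are planned, and development had already ceased (SAP sections 3.5, 4, 9 and 11.3). The protocol calls RECIST and GCIG PFS supportive. CA-125 results, target, non-target and new lesions, and deaths each have their own listing, so an NE entry hides no data. Phase 1 subjects without measurable disease still have progression scored under GCIG through SAP Table 5, from CA-125, non-target disease and new lesions. Appendix C itself says that CA-125 progression after relapse therapy is not validated. All of this stands and limits the weight of the point. It does not remove the contradiction: PFS is derived and listed per subject, and the entries would be wrong by the plan's other rules.

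A reader might infer more. One stronger reading is that the SAP plainly makes every subject with low baseline CA-125 NE, so that the third progression rule can never be used. The wording allows that but does not settle it, as step 3 shows. Another is that GCIG PFS then describes a worse-prognosis subset with a shorter median. The documents give neither the share of subjects below 2 x ULN nor their prognosis relative to the rest. If prognosis is the same there is no shift, only fewer subjects. This SAP also reports no GCIG PFS median that could be shifted.

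**Conclusion.** The point holds in a limited form. For Phase 1 subjects without measurable disease the exclusion from mRECIST and RECIST PFS is explicit. It departs from Appendix B, from the FAS and from the protocol's PFS rules, and it is undeclared. For subjects not evaluable by GCIG, the loss of RECIST progression and deaths from GCIG PFS follows under either meaning of the term. Whether the term includes a baseline CA-125 below 2 x ULN is an ambiguity that the SAP must resolve.

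The effect is limited to listed PFS: mRECIST and RECIST PFS in Phase 1, and GCIG PFS in both phases. The documents do not say how many subjects are involved, and neither the size nor the direction of any bias can be determined from them. The conclusion assumes that endpoint derivations means what it says and includes PFS. If the sponsor meant response only, the defect is one of wording and the same correction removes it.

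**What to change.** In SAP section 7:

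- Limit the NE rule to response-based endpoints: BOR, ORR, DCR and DOR.
- State that the 2 x ULN baseline threshold governs CA-125 response only, and that the section 6.4 flag does not decide entry into PFS.
- Derive PFS under each criterion for all treated subjects, with the existing censoring rules.
- For RECIST and mRECIST PFS without measurable disease, take events from non-target progression, new lesions or death.
- For GCIG PFS, take events from RECIST progression, death and the three CA-125 progression rules, disregarding CA-125 values affected by mouse antibodies or by peritoneal or pleural interference, as Appendix C requires.

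If the sponsor prefers to keep any exclusion from PFS, it should be listed in SAP section 9 with a reason. The cost is a few sentences and a small change to the PFS derivation. The data are already collected and listed.

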7.1. Efficacy Endpoints and Analyses

Refer to Section 2 for further details on Phase 1 and Phase 2 efficacy endpoint hierarchy.

Objective Response Rate

For purposes of mRECIST based derivations, a subject's best overall response (BOR) is determined by the highest qualitative value assessed during the study given a hierarchy of overall response results: CR > PR > SD > PD > NE. In order for a valid value of SD to be assigned, there must be evidence of stable disease for at least 8 weeks. If the minimum time for SD has not been met on the first assessment, the assignment of BOR will depend on subsequent response assessments. Subjects which do not have follow up data after a first assessment of SD prior to the minimum time requirement will be considered as not evaluable. BOR will be based on assessments collected after the first dose of study until confirmed disease progression; assessments collected after the start of new cancer treatment will not be considered.

The objective response rate (ORR) is defined as the number of subjects who exhibit a BOR response of CR or PR divided by the number of evaluable subjects. Subjects who discontinue prior to any evaluation of post-baseline tumor assessments will be considered as non-responders regardless of discontinuation reason. ORR will not be reported in the CSR synopsis.

BOR will be listed for each subject.

Progression-Free Survival

PFS is defined as the number of weeks from the date of first dose of study treatment to the first date of objectively determined progressive disease or death from any cause and is computed as described in Section 5.3. The primary analysis of PFS will include tumor assessments collected after the end of study treatment and will be based on mRECIST criteria for progressive disease confirmation. Tumor assessments taken after switch to another anti-cancer therapy will be excluded from consideration.

The first date of objectively determined progressive disease would be the earliest date of any post-baseline overall response finding of progressive disease is confirmed as part of the tumor lesion assessment data or death, unless a subject is censored at an earlier date. If an assessment occurs over several days, the method described in Section 5.6 will be used. If there are no adequate assessments for a subject, they will be censored on their first dose date unless they died prior to having their first assessment (in which case they will be considered to have had a PFS event of death). If a subject receives subsequent anticancer therapy prior to documentation of

Sponsor: Aduro Biotech, Inc.
Protocol Number: ADU-CL-11
Version and Date: Version 1.0, 03MAY2018

progressive disease, PFS will be censored at the latest adequate assessment prior to therapy initiation.

Subjects who progress or die following an extended period of follow up will also be censored at a latest adequate assessment prior to the end of a predefined lapse window, even if information is available regarding progression or death after this extended period. Should a subject die after the end of this lapse window they will be censored at their first dose date. The lapse window after which PFS events will not be considered is defined in Section 5.7.

If a subject does not receive confirmation of radiologically identified PD, and there are no further assessments prior to censoring, the subject will be considered to have progressed based on their last valid assessment.

Otherwise, if a subject does not have documented progression, the subject will be censored at the latest adequate assessment.

PFS will be listed for each subject.

Disease Control Rate

Disease control rate (DCR) is defined as the number of subjects who exhibit a BOR response of CR, PR or SD divided by the number of evaluable subjects.

The derivation analysis of DCR will be produced based on mRECIST, RECIST 1.1, and GCIG CA-125 criteria. A description of BOR derivations for RECIST 1.1 and GCIG CA-125 can be found in a previous section.

DCR will not be reported in the CSR synopsis. BOR will be listed for each subject.

Duration of Response

Duration of response (DOR) will be computed for subjects who have been identified as a responder (achieved an overall response of CR or PR during the PFS observation period); it will be computed as described in Section 5.3, where the reference date will be the first date where a subject has been documented to have achieved a responder designation. Censoring algorithms similar to those identified for PFS will be used for DOR.

The derivation of DOR will be conducted based on RECIST 1.1 and GCIG CA-125 criteria.

DOR will not be derived if there are no responders on the study.

Objective Response Rate Based on RECIST 1.1 and GCIG CA-125

For purposes of RECIST v1.1 derivation, the BOR will be based on methods described in Section 7.1 but with alternate assumptions around study treatment discontinuation; assessments following an initial, radiologically identified overall response of PD will not be considered regardless of confirmation status.

Sponsor: Aduro Biotech, Inc.
Protocol Number: ADU-CL-11
Version and Date: Version 1.0, 03MAY2018

For purposes of GCIG CA-125 derivation, BOR will be evaluated over the course of the study based on the method described in 7.1, using overall responses as defined in

Table 4 (for subjects with measurable disease at baseline) and **Table 5** (for subjects who did not have measurable disease at baseline).

For both methods, ORR remains defined as the percentage of subjects identified to have responded (CR or PR) for BOR.

The analyses specified in Section 7.1 for ORR will be repeated for ORR based on RECIST v1.1 and GCIG CA-125 criteria.

Overall Survival

Overall survival (OS) is defined as the number of weeks from the date of first dose of study treatment to the date of death from any cause and is computed as described in Section 5.3. Subjects still alive as of the data cut-off date will be censored on the last known alive date from mortality status follow up. For subjects that are lost to follow up, the last visit in the database or last contact date where the subject is documented to be alive will be used to estimate last known date alive.

Progression-Free Survival Based on RECIST 1.1 and GCIG CA-125

The analyses specified in Section 7.1 for PFS will be repeated for PFS based on RECIST v1.1 and GCIG CA-125 criteria.

